#### **14.6.2 Vital signs and body weight**

Summary statistics as well as scatter plots before and after treatment will be presented.

#### **14.6.3 Laboratory tests**

For quantitative values, summary statistics as well as scatter plots and shift tables before and after treatment will be presented.

For qualitative values, the number and percentage of subjects as well as shift tables before and after treatment will be presented.

#### **14.6.4 Dependency assessment**

The number and percentage of subjects with or without dependency will be presented.

### **14.7 Timing of Analyses**

When all data obtained in the double-blind period are locked, an interim analysis of the data in the double-blind period will be performed. When data obtained up to Week 34 of the extension period are locked, interim tabulation of the data up to Week 34 will be performed. When all data obtained in the extension period are locked, the final tabulation of the data over the entire study period will be performed.

## **15. Compliance with the Protocol, etc.**

### **15.1 Agreement on the Protocol**

To confirm the agreement on the content of the protocol and the compliance with the protocol, the principal investigator will affix their name and seal to or sign, and date the protocol or an alternative document.

### **15.2 Amendment of the Protocol**

The sponsor will revise the protocol as necessary when becoming aware of information on the quality, efficacy, and safety of the test drug and other important information for the proper conduct of the study. In such cases and in cases where the protocol is revised on the order of the head of the study site based on IRB's opinion, the sponsor will agree with the principal investigator on the revision of the protocol.

The principal investigator or subinvestigator must not implement any deviation from or changes of the protocol unless the principal investigator obtains prior written agreement from the sponsor and written approval from the IRB based on its prior review, except where medically necessary to eliminate immediate hazards to subjects, or when the change involves only administrative aspects of the study.

### **15.3 Deviation from the Protocol**

The principal investigator or subinvestigator will document all deviations from the protocol.

When having implemented a deviation from or a change to the protocol to eliminate immediate hazards to subjects or for other inevitable medical reasons, the principal investigator will submit a document describing the deviation or change and the reason for it, as well as a proposed protocol revision when protocol revision is necessary, as soon as possible, to the sponsor, the head of the study site, and the IRB via the head of the study site. By doing so, the principal investigator will obtain approval from the head of the study site and written agreement from the sponsor via the head of the study site.

## **16. Direct Access to Source Documents**

### **16.1 Source Documents and Source Data**

“Source documents” refer to information on the course of events in the study as well as original documents, data, and records that contain source information for case report forms. More specifically, source documents refer to records, such as informed consent forms, subject’s medical records, laboratory data, and study treatment records, necessary for the reconstruction and evaluation of the course of events in the study.

“Source data” refer to all information recorded in the original records on clinical findings, observations, and other activities in a clinical study and their certified copies, which are necessary for the reconstruction and evaluation of the course of events in the clinical study. “Source data” are contained in the source documents (original records or their certified copies).

Source data must be attributable, legible, contemporaneous, original, accurate, and complete, and any changes made to the source data may be traceable and may not obscure the original entry.

## **16.2 Direct Access**

The head of the study site and the principal investigator must allow monitoring and auditing by the sponsor and inspections by the IRB and regulatory authorities in and outside Japan, providing direct access to source documents.

The sponsor will confirm that each subject has consented in writing to direct access to their original medical records at the time of monitoring, auditing, and inspections by the IRB and regulatory authorities in and outside Japan.

## **16.3 Consistency Between Source Documents and Case Report Forms**

The sponsor will confirm that the entries in case report forms completed by the principal investigator and study-related records such as source documents are accurate by checking them against each other.

The entries in case report forms must be consistent with the contents in source documents. The principal investigator will prepare a record explaining the reason for any discrepancy between case report forms and source documents and submit the record to the sponsor. A copy of the record will be retained at the study site.

# **17. Quality Control and Quality Assurance for the Study**

The sponsor will implement quality control and quality assurance for this study according to the standard operating procedures. The sponsor's auditor will assess whether this study is being conducted in compliance with GCP, protocol, and written procedures, independently and separately from the routine monitoring and study quality control activities.

# **18. Ethics**

## **18.1 Compliance with GCP**

This study will be conducted in accordance with the ethical principles that have their origin in the latest Declaration of Helsinki and in compliance with Article 14-3 and Article 80-2 of the Law for Ensuring the Quality, Efficacy, and Safety of Drugs and Medical Devices, the standards related to the conduct of clinical studies of drugs stipulated by the Ministry of Health, Labour and Welfare, the MHLW Ordinance on Good Clinical Practice, and this protocol.

## **18.2 Protection of Subject Confidentiality**

The head of the study site will take necessary measures to guarantee the protection of subject confidentiality. Sufficient care for the protection of human rights will be taken, including identification of subjects by subject identifiers in documentation of subject data in the case report form. In addition, measures will be taken to ensure that subject confidentiality is protected when the monitors, auditors, IRB, and regulatory authorities access the subjects' source data.

## **18.3 Compensation to Subjects**

- 1) The study site will provide treatment or other necessary measures for a subject experiencing any study-related injury.

---

- 2) If a subject makes or may make a claim for compensation or indemnification from the study site for a study-related injury, the study site will immediately notify the sponsor, and the study site and the sponsor will cooperate to settle the issue.
- 3) The sponsor will compensate a subject experiencing any study-related injury in accordance with the compensation rules specified by the sponsor.
- 4) If responsibilities arise later for damage from a study-related injury to a subject in this study, the compensation will be the responsibility of and at the expense of the party liable for the damage.
- 5) The sponsor will insure against the compensation or indemnification mentioned above.

## 19. Data Handling, and Record Keeping

### 19.1 Preparation and Submission of Case Report Forms

In this study, clinical study data on investigations, observations, tests, and evaluations will be collected and recorded electronically to complete case report forms. The principal investigator or subinvestigator will complete case report forms for all subjects who have provided informed consent, and the principal investigator will review all entered data. For subjects not entering into the double-blind period, at least the information on the date of written informed consent, sex, year and month of birth, race, adverse events, and discontinuation of the study will be collected and recorded in the case report form. Case report forms will be completed as instructed separately in the written procedure.

### 19.2 Recording of the Symptom Diary

Subjects will record their symptoms in the symptom diary based on the electronic diary system. Data recorded by subjects will be transferred to electronic case report forms, and the case report forms will be regarded as source documents. The contents of the case report forms will be checked by the principal investigator, subinvestigator, or clinical research coordinator during interviews and when necessary. The symptom diary will be recorded as instructed separately in the written procedure.

### 19.3 Submission of 12-lead ECG charts

If any abnormal finding corresponding to an adverse event is observed in a subject after administration of the study drug and the sponsor considers it necessary to do so, the principal investigator or subinvestigator will submit copies of all ECG charts for the subject obtained during the study to the sponsor.

### 19.4 External Data

If obtaining any measurements at an external laboratory testing facility as electronic data, the sponsor will obtain such electronic data directly from the external laboratory testing facility. The method and time of data generation will be in accordance with a procedure established between the sponsor and the external laboratory testing facility.

---

## 19.5 Record Keeping

### 19.5.1 Study site

The head of the study site will retain study-related documents and records until notified by the sponsor that the retention of study-related documents and records is no longer necessary. The head of the study site or the record retention manager will take measures to prevent the loss or disposal of these records during a time period of retention and to make these records available upon request.

The principal investigator will retain study-related documents, as instructed by the head of the study site.

### 19.5.2 Institutional review board

The founder of the IRB will retain study-related documents and records until notified by the sponsor that the retention of study-related documents and records is no longer necessary. These records must be made available upon request from the regulatory authorities.

### 19.5.3 Notice from the sponsor

When the retention of study-related documents and records by the head of the study site or the founder of the IRB is no longer needed, the sponsor will notify the head of the study site and the founder of the IRB via the head of the study site.

## 20. Monetary Payment

The study site and the sponsor will discuss any monetary payment to a subject in advance and obtain approval of the IRB. If the IRB's approval is obtained, money should be paid to the subject based on the documented rules for payment to subjects.

## 21. Publication Policy

Information, including unpublished data included in this protocol, is the property of the sponsor and may not be disclosed to any third party without written consent of the sponsor. Disclosure of the results of the study to outside parties such as academic societies or journals, in part or in whole, will require the prior approval of the sponsor.

## 22. Study Administrative Structure

This study will be planned and conducted by the organizations described in the separate volume of the protocol. The separate volume will be revised separately from this protocol.

## 23. History of Protocol Amendments

Version: 1.0: created on October 28, 2020

## 25. Appendices

### Appendix 1 NRS (numerical rating scale)

### Appendix 2 Shiratori's severity criteria

Severity	Daytime symptom	Nighttime symptom
4: Severe itching	Intolerable itch, not relieved by scratching but instead worsens. Cannot focus on work or study.	Can hardly sleep because of itch. Scratching all the time, but itch intensifies with scratching.
3: Moderate itching	Scratching even in the presence of others. Irritation as a result of itch, continuous scratching.	Wake up because of itch. Can fall asleep again after scratching, but continue to scratch unconsciously while sleeping.
2: Mild itching	Itch sensation is relieved by light, occasional scratching. Not too disturbing.	Feel somewhat itchy, but can obtain relief by scratching. Do not wake up because of itch sensations.
1: Slight itching	Feel itchy sometimes, but tolerable without scratching.	Feel slightly itchy when going to sleep, but do not need to scratch. Sleeping well.
0: No symptom	Hardly feel itchy or do not feel itchy at all.	Hardly feel itchy or do not feel itchy at all.

Source: Shiratori A, et al., Clinical Evaluation of Oxitamide for Pruritus—Multicenter, Double-blind Study—, Nishinohon Journal of Dermatology 1983;45:1042-51.

### Appendix 3 New York Heart Association (NYHA) Classification

Class I: Patients with cardiac disease but without resulting in limitation of physical activity.

- Ordinary physical activity does not cause undue fatigue, palpitation, dyspnea, or anginal pain.

Class II: Patients with cardiac disease resulting in slight limitation of physical activity. They are comfortable at rest.

- Ordinary physical activity results in fatigue, palpitation, dyspnea, or anginal pain.

Class III: Patients with cardiac disease resulting in marked limitation of physical activity. They are comfortable at rest.

- Less than ordinary activity causes fatigue, palpitation, dyspnea, or anginal pain.

Class IV: Patients with cardiac disease resulting in the inability to carry on any physical activity without discomfort.

- Symptoms of heart failure or the anginal pain may be present even at rest. If any physical activity is undertaken, discomfort increases.

**Appendix 4 Specific signs or symptoms**

- 1) Dizziness (e.g., lightheadedness, vertigo)
- 2) Syncope (e.g., fainting spells)
- 3) Palpitation (e.g., heart pounding)
- 4) Tachycardia (as per vital sign assessment)
- 5) Falls (including fractures due to falls)
- 6) Seizures (including convulsions)
- 7) Gait disturbance (e.g., unsteady gait, unsteady on feet while walking)
- 8) Mental status change (e.g., patient appears confused, spatially or temporally disoriented, forgetful)
- 9) Somnolence (e.g., patient appears sleepier, drowsy, sedated, groggy)
- 10) Mood changes (e.g., patient appears more anxious, agitated, aggressive, uncooperative, restless, withdrawn)

**Appendix 5 Skindex-16**

During the past 1 week, how often have you been bothered by the following?

1. Skin itching
2. Skin burning or stinging
3. Skin hurting
4. Skin irritated
5. Persistence or recurrence of condition
6. Worry about condition (e.g., that it will get worse)
7. Appearance of skin
8. Frustration about skin
9. Embarrassment about skin
10. Annoyed about skin
11. Feeling depressed
12. Effect of skin on interaction with others (e.g., family members, friends, familiar people)
13. Effect of skin in desire to be with people
14. Skin making it hard to show affection
15. Effect of skin on daily activities
16. Skin making it hard to work/have enjoyment

No. 1 to 4 are categorized into questions concerning symptoms, No. 5 to 11 are categorized into questions concerning emotions, and No. 12 to 16 are categorized into questions concerning functioning. Patients choose one answer to each question from among 7 scales, where 0 indicates never bothered and 6 indicates always bothered.

Copyright holder for the Japanese version: Higaki Y (Tokyo Women's Medical University),  
Publisher: Medical Professional Relations K.K.

## Appendix 6 5-D itch scale

1. Duration

During the past 2 weeks, how many hours a day have you been itching?

Less than 6 hours/day, (2) 6-12 hours/day, (3) 12-18 hours/day, (4) 18-23 hours/day, (5) All day

2. Degree

Rate the intensity of your itching over the past 2 weeks.

(1) Not present, (2) Mild, (3) Moderate, (4) Severe, (5) Unbearable

3. Direction

Over the past 2 weeks, has your itching gotten better or worse compared to the previous month?

(1) Completely resolved, (2) Much better, but still present, (3) Little bit better, but still present, (4) Unchanged, (5) Getting worse

4. Disability

Rate the impact of your itching on the following activities over the past 2 weeks.

## • Sleep

(1) Never affects sleep, (2) Occasionally delays falling asleep, (3) Frequently delays falling asleep, (4) Delays falling asleep and occasionally wakes me up at night, (5) Delays falling asleep and frequently wakes me up at night

## • Leisure/Social

(1) Never affects this activity, (2) Rarely affects this activity, (3) Occasionally affects this activity, (4) Frequently affects this activity, (5) Always affects this activity, (\*) Not applicable

## • Housework/Errands

(1) Never affects this activity, (2) Rarely affects this activity, (3) Occasionally affects this activity, (4) Frequently affects this activity, (5) Always affects this activity, (\*) Not applicable

## • Work/School

(1) Never affects this activity, (2) Rarely affects this activity, (3) Occasionally affects this activity, (4) Frequently affects this activity, (5) Always affects this activity, (\*) Not applicable

5. Distribution

Mark whether itching has been present in the following parts of your body over the past 2 weeks. If a body part is not listed, choose the one that is closest.

Head/Scalp ( ), Face ( ), Chest ( ), Abdomen ( ), Back ( ), Buttocks ( ), Thighs ( ), Lower legs ( ), Tops of feet/Toes ( ), Soles ( ), Palms ( ), Tops of hands/Fingers ( ), Forearms (below the elbow) ( ), Upper arms (from the elbow to the shoulder) ( ), Points of contact with clothing (e.g., waistband, undergarment) ( ), Groin ( )

Source: Ebata T, et al., Development of the Japanese Version of the 5-D itch scale, Japanese Journal of Dermatology 2015;125,1035-40.

## Appendix 7 Patient Global Impression of Change (PGIC)

- 1) Very much improved
- 2) Much improved
- 3) Minimally improved
- 4) No change
- 5) Minimally worse
- 6) Much worse
- 7) Very much worse

## Appendix 8 Dependency assessment

Questionnaire on the study drug (before dialysis at Weeks 18, 34, and 58 or at the time of discontinuation)

Question	Remarkable	Moderate	Slight	None	Remarks Specify reason for Remarkable and Moderate
Do you feel clearheaded when using the study drug?					
Do you feel indifferent to disliked persons or things when using the study drug?					
Do you become hyperactive or talkative when using the study drug?					
Do you become broad-minded when using the study drug?					
Do you feel intoxicated when using the study drug?					
Do you feel irritable or somewhat lonely when the effect of the study drug runs out?					
Do you want to continue using the study drug?					 To relieve pruritus  To improve mood
Do you think this drug has become less effective?					
Do you want to use the study drug in larger doses?					 To relieve pruritus  To improve mood
Do you feel nauseated or tremulous when the effect of the study drug runs out?					

Adapted from Literature Reference 18)

Questionnaire on the study drug (at Week 59 or at Week 1 after discontinuation)

Question	Remarkable	Moderate	Slight	None	Remarks Specify reason for Remarkable and Moderate
Did you feel irritable or unstable after you discontinued the study drug?					
Did you have more difficulty in sleeping after you discontinued the study drug?					
Did you have nausea, vomiting, tremors of limb or perspiration after you discontinued the study drug?					
Do you really want to use the study drug?					 To relieve pruritus  To improve mood
Did you have convulsions after you discontinued the study drug?					
Did you have a clouded mind or heard or seen anything unusual after you discontinued the study drug?					

Adapted from Literature Reference 18)

Statistical Analysis Plan

Title of Study: A phase III clinical study of MR13A9 in previously treated hemodialysis patients with pruritus

Protocol No.: MR13A9-5

Version: 3.0

Date of Creation/Amendment: October 24, 2022

Sponsor: Kissei Pharmaceutical Co., Ltd.

Confidentiality Statement

This confidential document contains the sponsor's proprietary information. Any unpublished information contained in the document may not be disclosed without written consent of the sponsor.

Table of Contents

1. Study Objectives.....	3
2. Analysis Sets	3
3. Analysis Groups.....	4
4. General Principles of Statistical Analysis.....	4
5. Handling of Data.....	5
6. Statistical/Analytical Issues.....	6
7. Definition of Derived Data.....	8
8. Disposition of Subjects	10
9. Demographic and Other Baseline Characteristics	10
10. Treatment Compliance.....	12
11. Efficacy	13
12. Safety	18
13. Software Used for Analysis.....	22
14. Tables, Figures and Listing Shells	22
15. Changes from the Clinical Study Protocol	22
16. History of Revision of Statistical Analysis Plan	24
17. Literature References	24

1. Study Objectives

The purpose of this statistical analysis plan is to provide details of the analyses described in “14. Statistical Analysis” of the clinical study protocol (Version, 1.0).

2. Analysis Sets

Analysis sets are defined as follows: When the full analysis set (FAS) and the per protocol set (PPS) are used as analysis sets, analyses will be performed based on the treatment to which each subject has been assigned. When the safety set (SS) is used as an analysis set, analyses will be performed based on the treatment provided to each subject actually.

- 1) FAS
Population of subjects given at least one dose of the study drug, meeting the inclusion criterion related to NRS score, and having a baseline mean NRS score.
- 2) PPS (only in the double-blind period)
Population of subjects excluding the following subjects from the FAS:
 - Subjects not meeting the inclusion criteria
 - Subjects meeting any of the exclusion criteria related to efficacy evaluation
 - Subjects withdrawing from the study before Week 4 in the double-blind period
 - Subjects given < 9 or > 15 doses of the study drug before Week 4 in the double-blind period
 - Subjects changing the dosage and administration of a conditionally permitted concomitant medication or newly using a conditionally permitted concomitant medication before Week 4 in the double-blind period
 - Subjects using a prohibited concomitant drug or therapy before Week 4 in the double-blind period
 - Subjects changing the frequency of dialysis per week or the hemodialysis method before Week 4 in the double-blind period
- 3) SS
Population of subjects given at least one dose of the study drug

Unless otherwise specified, the analysis sets for endpoints and analysis items in the double-blind period and entire study period are as specified in [Table 2-1](#) and [Table 2-2](#).

Table 2-1 Analysis sets for endpoints and analysis items in the double-blind period

Endpoints	Analysis items	Analysis sets
Demographic and other baseline characteristics	Subject demographics	FAS, PPS, SS
	Other	SS
Treatment compliance	All items	FAS, SS
Efficacy	Primary variable (primary analysis)	FAS (primary analysis set), PPS
	Other	FAS
Safety	All items	SS

Table 2-2 Analysis sets for endpoints and analysis items in the entire study period

Endpoints	Analysis items	Analysis sets
Demographic and other baseline characteristics	Subject demographics	FAS, SS
	Other	SS
Treatment compliance	All items	FAS, SS
Efficacy	All items	FAS
Safety	All items	SS

3. Analysis Groups

The analysis sets and subjects included in the analysis sets for the analysis groups in the double-blind period are shown in [Table 3-1](#). The analysis sets and subjects included in the analysis sets for the analysis groups in the entire study period are shown in [Table 3-2](#).

Table 3-1 Analysis sets and subjects included in the analysis sets for the analysis groups in the double-blind period

Analysis groups	Analysis sets	Subjects included in the analysis set
MR13A9 0.5 µg/kg group	FAS, PPS	Subjects randomized to MR13A9 0.5 µg/kg
	SS	Subjects given MR13A9 0.5 µg/kg
Placebo group	FAS, PPS	Subjects randomized to placebo
	SS	Subjects given placebo

Table 3-2 Analysis sets and subjects included in the analysis sets for the analysis groups in the entire study period

Analysis groups	Analysis sets	Subjects included in the analysis set
MR-MR group	FAS	Subjects randomized to MR13A9 0.5 µg/kg in the double-blind period and entering into the extension period
	SS	Subjects given MR13A9 0.5 µg/kg in the double-blind period and entering into the extension period
P-MR group	FAS	Subjects randomized to placebo in the double-blind period and entering into the extension period
	SS	Subjects given placebo in the double-blind period and entering into the extension period

4. General Principles of Statistical Analysis

- All statistical tests will be performed using a two-sided significance level of 5%; however, a two-sided significance level of 15% will be used for the analysis of between-group demographic imbalance.
- Summary statistics to be presented include the number of subjects, mean, standard deviation, minimum, median, maximum, and quartile.
- For the double-blind period, data from the start of the screening period to the end of the double-blind period will be analyzed. Over the entire study period, data from the start of the screening period to the end of the follow-up period will be analyzed.
- Unless otherwise specified, data will be summarized by group and time point for each of the double-blind and entire study periods.

5. Handling of Data

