### **5.2 Extension Period**

Subjects meeting all of the following criteria for entrance at the Week 6 visit during the double-blind period will enter into the extension period. Subjects not meeting the criteria for entrance will be withdrawn from the study and undergo the assessments at discontinuation promptly.

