#### **5.2.1 Criteria for entrance**

- 1) Subjects not withdrawn during the double-blind period
- 2) Subjects receiving at least 14 doses of the study drug during the double-blind period
- 3) Subjects completing at least 70% of the symptom diary during the double-blind period

---

4) Subjects who are not inappropriate to enter into the extension period for safety or other reasons in the opinion of the principal investigator or subinvestigator

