**Table 14.2.2-1 Analysis sets and subjects included in the analysis sets for the analysis groups**

Analysis Groups	Analysis Sets	Subjects included in the analysis set
MR-MR group	FAS	Subjects randomized to MR13A9 0.5 µg/kg in the double-blind period and entering into the extension period
	SS	Subjects given MR13A9 0.5 µg/kg in the double-blind period and entering into the extension period
P-MR group	FAS	Subjects randomized to placebo in the double-blind period and entering into the extension period
	SS	Subjects given placebo in the double-blind period and entering into the extension period

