#### **14.6.1 Adverse events and adverse drug reactions**

For the double-blind period, analysis will include events occurring between the start of study treatment in the double-blind period and the end of the double-blind period. For the entire study period, analysis will include events occurring between the start of study treatment in the double-blind period and the end of the follow-up period.

Adverse events of special interest will also be summarized in the same manner.

1) Incidence of adverse events and adverse drug reactions

The number of events, the number of subjects experiencing events, the incidence of events and its two-sided 95% confidence interval will be presented. For the double-blind period, a Fisher's exact test will be used for comparisons between the placebo group and the MR13A9 0.5 µg/kg group, and the between-group difference in incidence and its 95% confidence interval will be presented.

2) Incidences of adverse events and adverse drug reactions (serious events and events leading to discontinuation)

The numbers of events, the numbers of subjects experiencing events, and the incidences of events will be presented for all events, events leading to death, serious events other than death, and events leading to discontinuation.

3) Occurrence of adverse events and adverse drug reactions

The number of subjects experiencing events and the incidence of events will be presented for all events and by primary SOC and PT.

4) Occurrence of adverse events and adverse drug reactions (by severity)

The numbers of events by severity will be presented for all events and by primary SOC and PT.

5) Occurrence of adverse events and adverse drug reactions (by time of onset)

For the entire study period, the number of subjects experiencing events and the incidence of events for all events and by primary SOC and PT will be presented by time of onset.

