 - 6 to 10: 3 points
 - 11 to 13: 4 points

- 14 to 16: 5 points
- Time to onset of an adverse event (days) = Date of onset of the adverse event – Start of study treatment + 1

8. Disposition of Subjects

Analysis for the double-blind period will include subjects who entered the double-blind period. Analysis for the entire study period will include subjects who entered the extension period.

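### The entire-period safety groups leave out MR13A9 subjects who stop by Week 6, and the by-onset table gives no row to the first six MR13A9 weeks of subjects switched from placebo

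*SAP*

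**What the plan says.** **Who is counted.** SAP Table 3-2 defines both entire-period safety groups, MR-MR and P-MR, by treatment received "in the double-blind period and entering into the extension period". Protocol Table 14.2.2-1 agrees; its P-MR safety group is "Subjects given placebo in the double-blind period and entering into the extension period". SAP 8 applies the same limit to disposition: "Analysis for the entire study period will include subjects who entered the extension period".

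**Who enters the extension.** Protocol 5.2.1 asks that the subject has not been withdrawn and has completed at least 70% of the diary. It also requires "Subjects receiving at least 14 doses of the study drug during the double-blind period" and "Subjects who are not inappropriate to enter into the extension period for safety or other reasons". Protocol 5.2 adds: "Subjects not meeting the criteria for entrance will be withdrawn from the study and undergo the assessments at discontinuation promptly".

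**Which events, on which clock.** Protocol 14.6.1 takes into the entire-period analysis "events occurring between the start of study treatment in the double-blind period and the end of the follow-up period". SAP 7 computes time to onset from the start of study treatment, and the footnote to SAP Table 5.7.1-1 makes that double-blind Day 1. Treatment duration in SAP 7 uses the same start.

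**The by-onset table.** Protocol 14.6.1 item 5 plans it for one period only: "For the entire study period, the number of subjects experiencing events and the incidence of events for all events". SAP Table 12.1.5-1 likewise lists only the entire study period. The rows of Table 12.1.5-2 are under 6, under 12, 12 to under 24, 24 to under 36, 36 to under 48, and 48 or more weeks. Each row counts subjects, not events.

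**The concern.** Entry to the extension depends partly on tolerability, so MR-MR is a selected group. A subject who stops MR13A9 for an adverse event in Week 3 belongs to neither entire-period group and cannot appear in the only table that shows when events begin. In P-MR the problem is the clock. The early rows describe placebo, and the start of MR13A9 treatment has no row.

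The protocol itself points to this stretch of treatment. Section 8.2.5 sets a six-week double-blind period for safety because, in MR13A9-4, every adverse drug reaction occurred before Week 6. A reader looking for the on-drug onset profile would see those weeks only in subjects who got through them (MR-MR) or mixed with placebo (P-MR). Losing early leavers tends to lower the MR-MR figures, and pooling placebo weeks tends to raise P-MR incidence. The net direction is therefore not known in advance.

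**Working it through.** **The plan's own figures.** Three doses a week give 3 × 6 = 18 double-blind and 3 × 52 = 156 extension doses, as stated. Week x falls on Day 7x + 1. Weeks 6, 12, 24, 36 and 48 are then Days 43, 85, 169, 253 and 337, which match the cut-points in Table 12.1.5-2.

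**P-MR on the drug clock.** Protocol 8.2.3 starts extension treatment at Week 6, nominally Day 43. Day on MR13A9 = study day − 42.

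| Row (weeks) | Study days | P-MR content |
|---|---|---|
| < 6 | 1–42 | placebo only |
| < 12 | 1–84 | 42 placebo days + 42 MR13A9 days |
| 12 to < 24 | 85–168 | drug days 43–126, i.e. weeks 6 to < 18 on drug |
| 24 to < 36 | 169–252 | weeks 18 to < 30 on drug |
| 36 to < 48 | 253–336 | weeks 30 to < 42 on drug |
| ≥ 48 | from 337 | from drug day 295, i.e. week 42 on drug (294 / 7) |

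No row equals Days 43–84, the first six weeks on MR13A9.

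**Can subtraction recover it?** All P-MR subjects reach the extension, so the first two rows share a denominator. The under-12 count minus the under-6 count gives subjects whose first onset of that event fell in Days 43–84. It misses those who had the event in both phases. Illustrations, assuming independent phases:

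- 30% affected in each phase: under-12 row = 0.30 + 0.30 − 0.09 = 51%. The difference is 51 − 30 = 21%, against a true 30%.
- 3% in each phase: 5.91% − 3% = 2.91%, against a true 3%.

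The loss is large for common events and the all-events row, and small for rare preferred terms.

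**Placebo share of P-MR.** Doses: 18 / (18 + 156) = 18 / 174 = 10.3%. Assuming doses on days 1, 3 and 5 of each week, the last falls on Day 7 × 57 + 5 = 404. A completer's treatment duration is then 404 days, of which 404 − 43 + 1 = 362 run from the first MR13A9 dose. The placebo part is 42 / 404 = 10.4%.

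**Early leavers.** No expected number is given.

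- Missing five or more of 18 doses bars entry (18 − 14 = 4 allowed).
- Loose bound: Protocol 8.6 plans 172 randomised and 100 completers at 58 weeks (58.1%). If exactly 100 complete, 0 to 72 across both arms could leave by Week 6.
- Closer guide: Protocol 1.3.2.2 reports treatment stopped or interrupted for events in 4 of 61 subjects at 0.5 µg/kg over 8 weeks in MR13A9-4. 4 / 61 = 6.6%, and 86 × 4 / 61 = 5.6 subjects.
- Assumed range of 3% to 15%: 2.6 to 12.9 of 86.
- Illustration: if 26 of 86 (30.2%) have an event and six of those leave before the extension, MR-MR shows 20 of 80 (25.0%). This assumes that every leaver had an event.

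**Does another rule bring leavers back?** SAP 12.1.5 keeps discontinued subjects in the denominator for rows within their tabulation period and drops them afterwards. It acts only inside MR-MR and P-MR, so it cannot restore subjects in neither group. In the under-6 row, events leading to discontinuation can include only subjects whose event began before Day 43 but who stopped after entering the extension.

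**The case against.** The strongest reply is that the early leavers are already reported. The double-blind safety set (SAP Table 3-1) includes everyone given MR13A9 and covers the same six weeks. SAP 12.1.1 to 12.1.4 and 12.1.6 tabulate its incidence, serious events, interruptions, discontinuations, severity and events of special interest, much of it beside a randomised control. SAP 12.6 adds subject lists. This stands: for leavers what is missing is the joined view by onset, not the events.

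Protocol and SAP also agree with each other, the by-onset table is descriptive, and no objective asks for a pooled exposed set. That is true, so this is a weakness of the analysis and not a contradiction.

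For P-MR, a reader can subtract 42 days from the clock and take the difference of two rows. That works approximately for rare terms, as shown above, but not for common events. It also does nothing for the entire-period incidence, severity and special-interest tables, which pool placebo and drug weeks. The double-blind tables offer no substitute, because they cannot contain P-MR's MR13A9 phase.

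The bound of 72 is loose. The figure of 100 completers comes from exposure guidance, not from a dropout forecast. The 4 of 61 is a better guide but is also imperfect: it includes interruptions, covers 8 weeks, and omits non-entry for missed doses or diary gaps.

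**Conclusion.** The concern holds. As the documents stand, no planned table gives adverse event incidence or onset for all MR13A9-exposed subjects from their first MR13A9 dose. In the by-onset table, the MR-MR under-6 row contains extension entrants only, the P-MR under-6 row is placebo, and P-MR's Days 43–84 have no row. The P-MR gap is the more serious part because nothing else in the plan fills it.

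The effect on any reported rate cannot be derived from the documents; the percentages for leavers and row subtraction rest on the stated assumptions. The structural figures (10.3% of P-MR scheduled doses, and 10.4% of a completer's treatment duration, on placebo) follow from the schedule. The overlap of the under-6 and under-12 rows is taken as printed, and the week and day columns agree. It should be fixed, but it does not touch the primary endpoint or the randomised six-week safety comparison.

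**What to change.** Keep the MR-MR and P-MR tables and add the following:

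1. A safety set of all subjects given at least one MR13A9 dose in either period, whether or not they entered the extension.
2. For that set, adverse event incidence, treatment duration and time to onset from the first MR13A9 dose to the end of follow-up, in non-overlapping rows that include 6 to under 12 weeks.
3. P-MR placebo-phase events shown separately, using the Weeks 1–6 and 7–58 split that SAP 10.4 already applies to dose.
4. A sentence in SAP 12.1 saying when the double-blind event window closes for a subject who withdraws. Events are collected through follow-up (Protocol 10.13.1.1), but SAP 5.7.2 addresses withdrawal only for final-assessment tabulations. A withdrawn subject's follow-up-week events may therefore enter no incidence table. The new set would capture them for MR13A9 subjects.

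The cost is programming, extra tables and an entry in SAP 15, since the set is not in Protocol Table 14.2.2-1. No new data are needed, and the double-blind Fisher comparison otherwise stays as it is. The new rates could look better or worse than the current tables.
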